Integrated Care - Our analyses indicate that 40% of all VHA enrollees were diagnosed with a MH disorder in FY11. The integration of MH treatments into PC settings is an evidence-based approach to managing common depression and anxiety disorders.^{1,2} True integrated care is based on the biopsychosocial model of illness in which both physical *and* mental illnesses are seen as the result of biological, psychological and social influences. With VHA's adoption of Patient Aligned Care Teams (PACT), the PC setting represents a health home, where all aspects of health care are delivered in a continuous, coordinated and patient-centered manner. Integration increases: 1) temporal access to MH care by making it available during PC encounters, 2) geographic access to MH care by making it available on-site in the PC clinic, and 3) cultural access to MH care by making it available in the less stigmatizing PC setting. In VA clinics where PC MH integration (PC-MHI) was deployed in FY07 and FY08, the detection, diagnosis and treatment of depression, anxiety, post-traumatic stress and substance use disorders increased significantly more than in clinics where PC-MHI was not deployed.³ Because of the greater geographic and cultural barriers to MH treatment in rural areas, the benefits of PC-MHI are even greater for the 41%⁴ of VHA enrollees who live in rural or highly rural areas. In fact, Veterans treated in CBOCs have significantly fewer MH encounters than Veterans treated at VA Medical Centers.⁵ Veterans treated in the smaller contract CBOCs have even fewer MH encounters than Veterans treated in VA staffed (i.e., owned and operated) CBOCs.⁶ Lack of engagement in MH care among rural Veterans may contribute to the higher MH severity levels⁷⁻⁹ and suicide rates¹⁰ observed among rural compared to urban VHA enrollees. Therefore, PC-MHI is critical to the well being of rural Veterans.

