Patient Recruitment: We will initiate recruitment at all sites 3 months into the first 6-month study period (labeled as “Identify Model” in the diagram above), during the implementation planning for Sites A and B. We will complete recruitment 3 months before the data analysis period begins. Thus, Veteran follow up will extend into the first 3 months of the data analysis period for all sites. Since the duration of the implementation period may vary from site to site, we will consider a site’s first referral to the Telemedicine Blended Model (with a PC-MHI telemedicine stopcode) as the index date with all Veterans enrolled prior to that date designated as controls and all Veterans enrolled after that date designated as intervention participants.

Figure 1: Implementation Timeline

Grant months	Identify Model	Intervention						Data Analysis
		6 months	6 months	6 months	6 months	6 months	6 months	
Site A	Implementation Planning	Implementation PDSA	Step Down					
Site B			Step Down					
Site C			Step Down					
Site D			Step Down					
Site E			Step Down					
Site F			Step Down					

Inclusion Criteria: We will sample from the patient population who screen positive on routinely administered VA MH screens (e.g., depression, alcohol, PTSD) at the 6 CBOCs, beginning 6

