Participant Recruitment and Consent: Using methods developed in a prior RCT we propose to extract appointment data from the Corporate Data Warehouse (CDW) and identify those Veterans with upcoming PC CBOC appointments scheduled at least one month in advance and who have no MH encounters in the previous 6 months. Real SSN access will be requested so that we can obtain contact information for potentially eligible patients. We are requesting a Waiver of Informed Consent and a Waiver of HIPAA Authorization for this initial phase of the recruitment process. We will send opt-out letters to the identified Veterans, noting that we may contact them about participation in a research study. Veterans may opt out by telephone or mail. On a daily basis, we propose to extract mental health screening data from the Corporate Data Warehouse and identify those Veterans who have not opted out of the study and who screen positive for alcohol abuse, depression, or PTSD. An RA will attempt to contact each such Veteran by telephone in order to conduct the informed consent process and complete the baseline interview. We are requesting a Waiver of Documentation of Informed Consent, as well as a HIPAA Waiver of Authorization for participation in the Effectiveness trial because we need to conduct the initial assessment interview as soon as possible after the clinical encounter with a positive screen. The study qualifies for these waivers because it is minimal risk, because it would not be practicable to conduct the study without the waivers (see above), because the research team will never be physically interacting with the participants in person, and the interaction with patients involves activities for which informed consent is not required when they occur in the course of standard clinical care (see Supplements L). When we send the opt-out letter, we will include information required for the informed consent process, so that the potential participants will have this available during the telephone contact. Those who are unable to understand or engage in the informed consent process (e.g., cognitive impairment, intoxication) will be excluded. The recruitment phase will last for 3 years. Opt-out letters will be sent to Veterans 3-4 weeks prior to the upcoming appointment. Those patients not opting out (by 1-800 telephone or mail) within two weeks, attend their primary care visit and screen positive for depression, alcohol, or PTSD during this visit will be contacted for recruitment. If we contact eligible patients who have not opted out of the study, but they state they cannot recall receiving the opt-out letter and study information, we will send another letter and study information sheet. We will contact them a week after the 2nd letter is mailed. This will ensure that we can reach them within the study recruitment window.

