CSQ-8	8 items to assess client satisfaction with MH services ⁷⁰

Note: The Perceived Access Inventory is currently being developed as the main product of a project led by [name], and is expected to be finalized in early 2016. In the Patient Survey document that contains copies of all the other questionnaires, there is a placeholder page for this survey. We will submit this questionnaire to the IRB once it is completed and before using it in our assessment interviews.

Measures Taken to Minimize/Avoid Bias, such as Randomization and Blinding

We will use CDW data and an opt-out approach to recruit a representative sample of Veterans meeting the eligibility criteria for the effectiveness trial. Sites will be randomized with regard to timing of implementation. Research assistants will be blind to the status of implementation at the sites.

Formative Evaluation: Qualitative Interviews with Veterans during Early Implementation and with Site Personnel [name]-Implementation

In order to minimize burden on sites, and because gold standard facilitation involves activities normally conducted for both pre-implementation and progress-focused formative evaluation (and thus will be completed as part of the quality improvement activities of Specific Aim 1), we will only conduct parts of the formative evaluation under Specific Aim 2. Specifically, study team members will conduct progress-focused interviews with a sample of eligible Veterans who receive PCMHI care early in the implementation effort at each site, and post-implementation interviews with site personnel, including the CBOC Executive Director, the study site champion, and any other relevant staff they recommend to us.

Veteran participant interviews:

Patients will be identified by the PC-MHI provider (co-located or tele-co-located), who will provide names and contact information via encrypted e-mail or telephone, or the list will be uploaded to a secure research sharepoint site at CAVHS. The potential patient participants will be sent an opt-out letter and recruited by phone if they do not opt-out (by 1-800 telephone or mail) within two weeks. Because we need to interview patient participants soon after they receive their mental healthcare, we are requesting a Waiver of Documentation of Informed Consent and a Waiver of HIPAA Authorization for participation in this study component. We will obtain verbal consent over the phone, and document that we have obtained verbal consent in the research record.

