CBOCs are the unit of randomization, with CBOCs randomized to an intervention start date using the stepped wedge design. A total of 6 CBOCs will participate in the study, with two CBOCs allocated to each of the 3 start dates. Randomization will be computer-generated by the statistician. A subset of potential patients (based on inclusion criteria) will be selected at each CBOC on a daily basis during the 5 measurement periods shown in Figure 1: Grant Activity Timeline (the formative evaluation control period(s), implementation, and step down period(s)).

Blinding

CBOCs and the research team will not be blinded to the intervention start dates. However, outcome assessment by independent evaluators (research assistants) will be blinded.

Statistical Analysis

The analyses will be conducted using the intention-to-treat principle, with CBOCs analyzed according to their randomized, crossover time irrespective of whether crossover took place at

the specified time. The results across the unexposed (control phase) observation periods will be compared with those across the observation periods in which the CBOCs are exposed to the Telemedicine Blended Model intervention (intervention phase). Characteristics of the patients and the CBOCs will be summarized by exposure status to examine potential selection bias or lack of balance.⁸¹ Because we have a small number (3) of randomization steps, we will compare numbers of patients analyzed, cluster (CBOC) size, CBOC characteristics and patient characteristics by randomization group. Patient-level data will be collected, with the primary analysis being patient-level.

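### Neither planned check for a change in patient mix between phases is adequate, and the Hypothesis 2 patient-level model has no patient covariates

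*Combined protocol and SAP*

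**What the plan says.** **Entry and phase.** Under Inclusion Criteria, "We will sample from the patient population who screen positive on routinely administered VA MH screens". Participant Recruitment and Consent adds that Veterans who have not opted out, and who "attend their primary care visit and screen positive for depression, alcohol, or PTSD during this visit will be contacted for recruitment". Under Patient Recruitment, phase is set by each site's first referral, with "all Veterans enrolled prior to that date designated as controls and all Veterans enrolled after that date designated as intervention participants". Under Blinding, "CBOCs and the research team will not be blinded to the intervention start dates".

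**Background.** The Integrated Care paragraph reports that where primary care mental health integration was deployed, "the detection, diagnosis and treatment of depression, anxiety, post-traumatic stress and substance use disorders increased significantly more" than where it was not.

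**Planned checks.** The Statistical Analysis section for Hypothesis 2 states that "Characteristics of the patients and the CBOCs will be summarized by exposure status to examine potential selection bias or lack of balance". The next sentence plans a second comparison, across the three randomization groups, of numbers analyzed, clinic size, and clinic and patient characteristics. Neither comparison is broken down by calendar period.

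**Model.** The patient-level model has fixed terms for intervention and six-month period and a random effect for CBOC. The only baseline adjustment mentioned there belongs to the CBOC-level analysis and concerns differences among clinics, not between phases. Interview Assessment Data says that demographics, barriers, perceived access and readiness are collected at baseline for casemix adjustment, but none of them appears in the Hypothesis 2 model.

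**The concern.** Eligibility arises after randomization, at clinics that are aware of their phase. If moving to integrated care changes how screens are given or who screens positive, the patients enrolled after crossover differ from those enrolled before, and randomizing start dates does not protect against that. The period term in the outcome model removes a common time trend. It does not remove a change in case mix that coincides with crossover.

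The outcome is a change score, which depends on where patients start. A shift in baseline MCS at crossover could therefore be read as a larger or smaller clinical effect. The protocol intends the result to inform wider implementation, so readers need a check that can tell selection from drift, and a model that does not rely on that check to reveal a problem.

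**Working it through.** The plan states no figure for this point, so there is none to reproduce.

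**Inputs.** From the Randomization and Power Calculation text: 6 CBOCs, 2 per start date, 3 start dates, 5 six-month periods, SD 10, ICC 0.01, 750 enrolled and about 600 analyzed. Patients per clinic-period: 750/(6 × 5) = 25, or 600/(6 × 5) = 20. Assumptions: equal cell sizes, crossover at period boundaries, drift common to all clinics, and the plan's ICC applied to baseline MCS. Figure 1 does not survive clearly in the text, so two layouts were tried.

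**Step 1: timing of the exposed and unexposed cells.**
- Crossover at periods 2, 3, 4: exposed mean = (14 + 12 + 9)/(4 + 3 + 2) = 35/9 = 3.89; unexposed mean = (1 + 3 + 6)/(1 + 2 + 3) = 10/6 = 1.67.
- Crossover at periods 3, 4, 5: 26/6 = 4.33 and 19/9 = 2.11.
- The gap is 2.22 periods in both, or 2.22 × 6 = 13.3 months.

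**Step 2: what the exposure-status table shows.** For a selection shift s and a drift d per period, the crude difference is s + 2.22d.

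| True shift s | Drift d | Crude difference | With period terms |
|---|---|---|---|
| 0 | -0.9 | -2.0 | 0 |
| -2 | 0 | -2.0 | -2 |
| -2 | +0.9 | 0.0 | -2 |

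Drift alone and selection alone give the same table, and together they can cancel.

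**Step 3: what the randomization-group table shows.** All groups span the same five periods, so common drift drops out. The exposed shares are 0.8, 0.6 and 0.4 (or 0.6, 0.4 and 0.2), so first minus last equals 0.4s. For m = 25:
- between-clinic variance = 0.01 × 100 = 1; variance of a cell mean within clinic = 99/25 = 3.96;
- variance of a clinic mean over five periods = 1 + 3.96/5 = 1.792;
- difference between two groups of two clinics: variance 2 × 1.792/2 = 1.792, SE 1.34;
- on the scale of s: 1.34/0.4 = 3.35, so 80% power needs 2.80 × 3.35 = 9.4 points.

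For m = 20 the figure is 9.9. At an ICC of 0.05, shown as a range, it is 16.8 to 17.1.

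**Step 4: the same check with period terms.** The generalized least squares SE of the exposure contrast in baseline MCS, with period terms and a random CBOC effect, is 1.34 (m = 25) or 1.48 (m = 20). The shift detectable with 80% power is 2.80 times that: 3.7 or 4.1 points (3.9 or 4.3 at ICC 0.05).

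**Step 5: illustrations of the effect on the outcome, on assumptions outside the documents** (higher MCS taken as better).
- Suppose screen-positives are the worst 25% on severity, detection rises 10% to 30%, severity correlates 0.6 to 1.0 with MCS, and change falls 0.5 point per point of baseline. The truncated-normal means then move baseline MCS up by 0.35 to 1.6 points, and the contrast moves by 0.2 to 0.8 points against the intervention.
- Suppose instead that exposed patients start 2 points lower and baseline and follow-up correlate at 0.4 to 0.7. Regression to the mean moves the contrast by (1 - r) × 2 = 1.2 to 0.6 points in favor of the intervention.

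The sign depends on the assumption made.

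**The case against.** The plan has real safeguards. Candidates come from appointments booked at least a month ahead, opt-out letters go out before the visit, positive screens are drawn centrally, and "Research assistants will be blind to the status of implementation at the sites". Clinic staff do not choose participants. The outcome estimate is itself period-adjusted and the time effect will be reported. The illustrated 0.2 to 0.8 points is only about 0.1 to 0.55 of an SE of 1.48. All of this stands. It narrows the open route to unblinded administration of routine screens and any change in who screens positive, but does not close it.

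Three stronger readings are tempting and are not supported:
- **That the exposure-status table is the only check.** The comparison by randomization group follows it directly. Its weakness is dilution, not absence.
- **That integrated care is shown to bring in milder cases, biasing the trial against the intervention.** The Background statement is a non-randomized comparison of detection, diagnosis and treatment. It gives neither positive rates nor severity on routine screens.
- **That the treatment effect is confounded with 13 months of calendar time.** That gap belongs to the unadjusted characteristics table. The outcome model has period terms.

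The period-adjusted check is also limited. For baseline shifts of 0.35 to 1.6 points its power would be about 6% to 22%.

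**Conclusion.** The point holds as a gap in the planned checks and in the model, not as a demonstrated bias. The exposure-status table compares patients about 13 months apart and cannot separate selection from drift. The randomization-group table avoids common drift but shows 0.4 of a shift and would need about 9.4 to 9.9 points for 80% power, more than twice the 4-point difference the trial is sized for. The plan states no action if an imbalance appears, and the casemix adjustment announced under Interview Assessment Data is missing from the Hypothesis 2 patient-level model.

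The timing gap and the factor 0.4 rest on the design and on equal cell sizes. The detectable shifts also rest on SD 10 and ICC 0.01. Any figure for bias in the treatment effect is an illustration only, and its direction is not known. The change is worth making because it is cheap, not because the trial is shown to be compromised.

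**What to change.** 1. **Model.** Add to the Hypothesis 2 patient-level model which index-visit screen or screens were positive, the score where held, and the casemix factors named under Interview Assessment Data. Include baseline MCS as a further covariate or in a sensitivity analysis: the interview can follow the visit by up to two weeks, so it may already reflect care begun that day. Perceived access and readiness share that timing, so also show the result without them.

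2. **Check.** Tabulate enrolled numbers and baseline characteristics by CBOC and period. Estimate the exposure contrast for each with the same CBOC and period terms as the outcome model, and report it with its interval, not as a pass/fail test.

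3. **Where approvals allow,** fit the same model to the screen-positive rate among attending Veterans and to the consent rate, from aggregate CDW counts. The plan describes this extraction for recruitment ("On a daily basis, we propose to extract mental health screening data from the Corporate Data Warehouse"), and the Administrative Data section does not list screening scores, so analysis use for non-consenters should not be assumed.

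**Cost.** Items 1 and 2 need SAP wording, a few model runs and a few extra covariates, using data held on enrolled patients. Item 3 may need further approval. The remaining limit is power: on enrollees' baseline MCS, item 2 has 80% power only for a shift of about 3.7 to 4.1 points. Item 1 is therefore worth having whatever item 2 shows.

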Veterans may benefit from knowing that their participation may be useful to VHA leaders who are seeking to improve mental healthcare and infectious disease care for patients receiving care in CBOCs; however, study participation in itself will not likely result in any direct benefit to participants.

Population to be Studied:

Human Subjects Involvement and Characteristics

Veteran Participants: For the Specific Aim 2 Formative Evaluation of the initial implementation at the 6 sites, which will assess adaptation of the Blended model to the CBOC setting during the implementation phase at each site, approximately 24 Veteran patients will be enrolled to participate in qualitative interviews. For the Specific Aim 2 Effectiveness test, we propose to enroll approximately 750 Veterans who screen positive on routinely administered VA MH screens (e.g., depression, alcohol, PTSD) at the 6 study CBOCs, for 18 months beginning at the first implementation period and continuing until the last two sites have completed the implementation phase (see methods section). Only those patients receiving specialty MH treatment in the 6 months prior to recruitment; those with a diagnosis of substance dependence; and those with a psychotic disorder diagnosis (schizophrenia, bipolar disorder, other psychotic disorders) will be excluded. Patients who consent to participate will participate in an initial assessment of health status by telephone and a follow-up telephone assessment six months later.

For the exploratory third aim at the CBOCs, up to 40 total Veterans will be enrolled to participate in qualitative interviews about their HCV or HIV/mental health treatment experiences and preferences. Two subsets of Veterans will comprise the total sample for this aim:

1. 20 Veterans diagnosed with HCV.
2. 20 Veterans diagnosed with HIV and screen positive on a depression screen.

Provider Participants: For post-implementation interviews (Specific Aim 2 Formative Evaluation), the CBOC director, site champion, and any other relevant staff they recommend to us at each of the 6 study CBOCs will be recruited to participate in qualitative interviews. The telehealth MHPs involved in the study will also be interviewed.

Inclusion of Non-Veteran Participants: All patient participants will be Veterans. Because some of the provider and manager participants will not be Veterans, the study will request approval to recruit non-Veterans.

Sources of Materials

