Because this is a cross-sectional design in which different patients are sampled at each step in the study, we do not need to include a random effects term for repeated measures on the same individuals. The effect size adjusted for calendar time and its 95% confidence interval will be calculated to assess the estimated change in outcomes after introduction of the intervention.

Although the primary analysis will be intention-to-treat, if necessary, we will include an analysis of what actually happened if the CBOCs do not crossover to the intervention at the original specified time.

Per Hemming et al.,⁸¹ we will report the estimated intra-cluster correlation for use in design of future trials. In addition, we will report the time effect from the fitted model to allow assessment of possible confounding effects of calendar time. We may include an effect modifier term in the model representing the length of the period up to the current observation during which the CBOC has been exposed to the intervention. This will allow examination of the way the impact of the Telemedicine Based care develops over time once introduced into the CBOC.

Power Calculation for Hypothesis 2. We calculated the sample size for the stepped wedge design following the approach of Woertman et al.,⁸⁶ which has been corrected by Hemming, Girling, and Taljaard.^{84, 87, 88}

We first determined the sample size needed if individuals were randomized (N_u). This is then multiplied by a design effect, DE_{sw} , to correct for both clustering and the stepped wedge design.

$$DE_{sw} = \frac{1 + \rho(tm + m - 1)}{1 + \rho(0.5tm + m - 1)} * \frac{3(1 - \rho)}{2(t - 1/t)}$$

where m is the number of subjects within a cluster in each measurement period, ρ is the intra-cluster correlation (ICC), t is the number of randomization steps, and k clusters are measured at each of T measurement periods. The required sample size for analysis using the stepped wedge design is then $N_{sw} = N_u * DE_{sw} * T$. Finally, we adjusted the required sample size formula to account for 20% attrition over the 6-month period to obtain the number of patients that need to be selected for assessment, N .

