In our study, the 6 CBOCs will be randomly allocated two at a time to one of the $t = 3$ randomization steps. Based on earlier work, the intracluster correlation coefficient, ρ will be estimated as .01. There will be a total of 5 measurements for each cluster, including the control period(s), implementation, and maintenance period(s) (see schematic diagram). We assumed for the power calculations that approximately $m=18$ participants would be available within each CBOC in each 6-month time interval.

The calculations are based on having 80% power at a significance level of 0.05 to detect a medium effect size (Cohen's $d=0.42$) between the usual care referral model (EU) and the Telemedicine Blended model intervention group (TB) in our primary outcome measure for the effectiveness hypothesis, MCS from SF-12V. This represents a difference of 4 points in the MCS scores between the referral model group and the Telemedicine Blended Model group, assuming a pooled standard deviation of 10. This gives the unadjusted total sample size, N_u , of 128 for the two-sided, two-sample t-test of equal means.

The total number of patients to be selected for assessment across the 6 CBOCs will be 750. This was determined after adjusting the total sample size required under individual randomization N_u , for the design effect, multiplying by the 5 measurement periods, and accounting for a 20% attrition rate. This will result in approximately 600 patients providing baseline and 6-month follow-up data for analysis, accounting for attrition.

The assumption of approximately 18-30 participants at each CBOC in each 6-month period does not represent the maximum that can be recruited at a site in any six-month period; it is a possible average based on our experience in the first six-months of recruitment. We will recruit all eligible participants at the study sites as described elsewhere in the protocol.

Direct Access to Source Data/Documents:

Only authorized persons will have access to the information gathered in this study. Authorized persons may include regulatory agencies such as, the Government Accounting Office (GAO) or the Office for Human Research Protection (OHRP), Office of Research Oversight (ORO), as well as members of the Research Administration staff of CAVHS.

Data Safety and Monitoring Plan:

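### The unadjusted sample size of 128 belongs to d = 0.50, not the stated d = 0.42 (which needs 180), and 4 points at SD 10 is d = 0.40; the 750 target itself fits d = 0.42

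*Combined protocol and SAP*

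**What the plan says.** All of this is in the combined protocol and SAP, under Data Analysis for Effectiveness (Hypothesis 2), Power Calculation for Hypothesis 2, unless noted.

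- **Effect size and power.** The target is 80% power at significance level 0.05 for Cohen's d = 0.42 on the primary effectiveness outcome, the SF-12V MCS. The plan explains the effect size thus: "This represents a difference of 4 points in the MCS scores" between the two care models, "assuming a pooled standard deviation of 10".
- **Unadjusted size.** The individually randomised total, N_u, is given as a figure "of 128 for the two-sided, two-sample t-test of equal means".
- **Inflation.** N_u is multiplied by a stepped wedge design effect and by the number of measurement periods. The sentence beginning "The required sample size for analysis using the stepped wedge design is then" gives N_u × DE_sw × T. The result is then raised for 20% attrition.
- **Inputs to the inflation.** ICC 0.01, t = 3 randomisation steps, T = 5 measurement periods and m = 18 participants per CBOC per period.
- **Result.** "The total number of patients to be selected for assessment across the 6 CBOCs will be 750", and "This will result in approximately 600 patients providing baseline and 6-month follow-up data for analysis". The enrolment target is repeated under Population to be Studied: "we propose to enroll approximately 750 Veterans who screen positive".
- **Cluster-period size.** A later paragraph widens m: "The assumption of approximately 18-30 participants at each CBOC in each 6-month period" is described as a possible average and not a ceiling.

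**The concern.** Two printed figures do not follow from the inputs printed beside them. The unadjusted total is too small for the stated d, and the stated d is not the ratio of the stated difference to the stated SD.

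This is the only power justification in the documents for the primary effectiveness outcome. A reader who starts from 128 and follows the stated steps does not arrive at 600 and 750, and could wrongly conclude that the trial over-enrols or that some further inflation was left out. Anyone who reused 128 with d = 0.42 would plan a comparison with about 65% power. The 80% power claim is also attached to a 4-point difference, for which the planned sample gives less.

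**Working it through.** **Inputs.** All come from the power section: two-sided α = 0.05, power 80%, d = 0.42, difference 4, SD 10, ρ = 0.01, t = 3, T = 5, m = 18, attrition 20%. Equal allocation in the individually randomised calculation is my assumption; unequal allocation would only raise N_u.

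**Step 1: unadjusted size (two-sample t-test, noncentral t).**

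| d | per group | total |
|---|---|---|
| 0.40 | 99.1 → 100 | 200 |
| 0.42 | 89.96 → 90 | 180 |
| 0.50 | 63.8 → 64 | 128 |

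The printed 128 is reproduced at d = 0.50. A one-sided test does not rescue it, since d = 0.42 would then need 142. With 128 patients, power is 80% at d = 0.50, 65% at d = 0.42 and 61% at d = 0.40.

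**Step 2: design effect.** The plan's formula is

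DE = [1 + ρ(tm + m − 1)] / [1 + ρ(0.5tm + m − 1)] × 3(1 − ρ) / [2(t − 1/t)]

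- m = 18: (1.71 / 1.44) × (2.97 / 5.333) = 1.1875 × 0.5569 = 0.6613
- m = 20: (1.79 / 1.49) × 0.5569 = 0.6690
- m = 30: (2.19 / 1.74) × 0.5569 = 0.7009

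**Step 3: analysed = N_u × DE × 5; selected = analysed / 0.8.**

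| N_u | m = 18 | m = 20 | m = 30 |
|---|---|---|---|
| 128 | 423 / 529 | 428 / 535 | 449 / 561 |
| 180 | 595 / 744 | 602 / 753 | 631 / 788 |
| 200 | 661 / 827 | 669 / 836 | 701 / 876 |

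The stated 600 / 750 is met by 180 at m = 18 to 20. It is not met by 128 at any m: as m grows without limit the design effect tends to (4 / 2.5) × 0.5569 = 0.891, and 128 × 0.891 × 5 / 0.8 = 713. Working back, 600 / (5 × 0.6613) = 181.5 and 600 / (5 × 0.6690) = 179.4, so the target implies N_u of about 180.

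**Step 4: difference, SD and d.** 4 / 10 = 0.40. At SD 10, d = 0.42 is 4.2 points. For 4 points to be d = 0.42, the SD would have to be 4 / 0.42 = 9.52.

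**Step 5: power with 600 analysed, plan's formula.** These use the equivalent N_u from step 3.

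| | DE at m = 18 | DE at m = 20 |
|---|---|---|
| d = 0.42 | 80.3% | 79.9% |
| d = 0.40 | 76.4% | 75.9% |
| detectable d at 80% | 0.418 | 0.421 |

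The m = 20 column is the coherent one for 600 completers, because 6 CBOCs × 5 periods × 18 = 540 and 6 × 5 × 20 = 600.

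**Step 6: check against the plan's mixed model.** I took the random intercept plus fixed period model, with 6 CBOCs, 5 equal periods, 20 analysed per CBOC-period, ICC 0.01 and SD 10. I assumed one all-control first period and two all-intervention final periods. The standard error of the intervention effect is 1.478. Power is 77% for 4.0 points and 81% for 4.2 points, and the difference detectable with 80% power is 4.14 points.

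**The case against.** The arithmetic in steps 1 to 3 is not open to dispute. The case on the other side concerns how much it matters.

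- **The 128 has no consequence for the trial.** It did not feed into 750, and enrolment, analysis and decision rule are unchanged. This stands. What remains is a derivation that cannot be reproduced as printed.
- **The 0.42 versus 0.40 gap may be rounding.** The difference and SD are whole numbers beside a two-decimal d; 4.2 rounds to 4 and 9.52 rounds to 10. This is possible, but the text does not say so, and the two readings give different power for a 4-point difference.
- **The shortfall is within the uncertainty of the planning inputs.** SD 10 and ICC 0.01 are assumptions. In the mixed model, power for 4 points is 77% at SD 10 and 81% at SD 9.52. This stands as a comment on size, but it does not make 80% the right figure for the inputs as printed.
- **Recruitment may exceed the plan.** With 30 enrolled per CBOC-period and 80% retained (24 completers), the mixed model gives 84% for 4 points at SD 10. With 18 completers it gives 73%. The 76% therefore applies to the stated 600 completers and not to every outcome the plan allows.
- **That 180 was intended is an inference.** It rests on back-calculation from 600. The inference is strong, because the stated d and the stated total both lead to 180, but the sponsor should confirm it.

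**Conclusion.** The point holds. N_u is printed as 128 where the stated inputs give 180, so it is 52 too low. The 750 target is consistent with d = 0.42 and is not undermined by this error.

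The pairing of d = 0.42 with 4 points at SD 10 is also wrong as written. For 4 points at SD 10 with 600 analysed, power is about 76% by the plan's formula and 77% from its mixed model. Against the claimed 80%, that is a shortfall of 3 to 4 percentage points. The difference detectable with 80% power is about 4.1 to 4.2 MCS points. The whole shortfall comes from the 0.42 versus 0.40 mismatch and none of it from the 128.

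These figures rest on the plan's ICC of 0.01, SD of 10, 20% attrition and five equal periods, and on equal allocation in the individually randomised step.

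**What to change.** In the power section:

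1. Replace 128 with 180, after the sponsor confirms that d = 0.42 was the input used.
2. Make the target effect consistent. Either state 4.2 points (d = 0.42 at SD 10) with 80% power, or keep 4 points at SD 10 (d = 0.40) and state about 76% power with 600 analysed.
3. As an optional tidy-up, state m as about 20 completers (25 enrolled) per CBOC-period, so that 6 × 5 × m gives 600 and 750. This moves the d = 0.42 total only from 744 to 753. The plan's range of 18 to 30 (540 to 900 in all) already contains both totals.
4. Keep 750.

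The cost is wording in one section and a slightly less favourable stated power or detectable difference. Enrolment, analysis and decision rule do not change.
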